In addition, there may still be several challenges when using WATs with frail older people. First, there is no guarantee that the users will encounter the BCTs, even if they are present in the WATs (Mercer et al., 2016). This is particularly true for frail older people, as some studies have shown that older people may be fearful of new technology and reluctant to use it (Jen & Hung, 2010; Deng, Mo & Liu, 2013). Second, the WAT still lacks several important BCTs, which are essential to increasing the self-efficacy and motivation of older people to engage in exercise and to take up new physical activities (French, Olander, Chisholm, & Mc Sharry, 2014; van Stralen, De Vries, Mudde, Bolman, & Lechner, 2009). Those BCTs that are lacking include action planning, problem solving, and the modelling of the desired health-related behaviour (Mercer et al., 2016).

To further strengthen the use of WATs among frail older people, it is suggested that some additional measures should be implemented. First, they should be provided with structured technical training, support, and reassurance on using the WATs and their related mobile applications, especially during the early stages of the programme. Second, more support, focusing on action planning, problem solving (i.e., both exercise-related and IT-related problems), and the modeling of health-related behaviour should be delivered in person alongside the WAT intervention and exercise training (Cramp & Byron-Daniel, 2012; Edmonds, McGuire, & Price, 2004; Neill, Belan, & Ried, 2006; Pinto, Frierson, Rabin, Trunzo, & Marcus, 2005). Third, these forms of support should be gradually withdrawn to see if the older people can use the WATs on their own.

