Interventions: A 3-month exercise programme plus WAT intervention will be arranged for the participants in the experimental group. They will receive a weekly centre-based exercise programme for 3 months. Meanwhile, two face-to-face sessions followed by weekly to monthly telephone sessions offering support on dealing with technical issues and BCTs will be arranged for the experimental group (see Figure 1: Intervention components for the experimental group). The additional technical support given alongside the WAT intervention will be gradually withdrawn from the participants. Eventually, all additional measures to support the use of WATs among participants will be stopped. Participants will be left to use the WAT on their own for 3 months during the follow-up period. Another 3-month exercise programme with face-to-face, and telephone-delivered BCTs follow-up sessions will be arranged for the control group, with the number and timing of all sessions similar to that in the experimental group. All face-to-face sessions and exercise training sessions will have ≤ 10 participants to maintain good interactions between the participants and the physical trainer / facilitator.

Wearable activity tracker (WAT)-based intervention for the experimental group: The aim is to strengthen the participants' motivation to develop the intention to gradually increase their physical activity levels to eventually meet the level recommended for older people by the American Heart Association (AHA)^[2]. The intervention consists of two face-to-face group-based sessions followed by a weekly to monthly telephone sessions offering support on technical issues and behavioural change techniques.

Supervision of face-to-face sessions and telephone follow up: JL (the PI), has successfully conducted many psychosocial intervention trials to enhance behavioural changes in older people with different health problems, and RK, who has experience in using WAT with older people. They will be responsible for implementing the face-to-face sessions and training an RA as a facilitator to deliver telephone BCTs support. A protocol for the face-to-face sessions and a script for telephone behavioral support will be developed and validated by the experts in BCTs and WAT. The initial calls by the RA will be observed by JL and feedback will be provided to maintain quality. Throughout the study, the telephone support will be supervised by JL and RK.

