Physical training in the experimental and control groups A weekly 45-60 minute structured exercise programme, designed according to the AHA's recommendations on exercise for older people^[2] will be conducted for 12 weeks in the community centres. The exercise sessions will begin with a brief warm-up, followed by 30 minutes of moderate-intensity walking, 30 minutes of light upper and lower body resistance training, balance, and flexibility exercises. All of the participants will receive circuit training with set exercises, but the dosage of different components will be tailor-made for each participant based on his/her physical condition. Exercise intensity will be individually monitored using a subjective 0-10 scale for physical exertion (Borg CR10 scale). The participants will be initially instructed to walk at a moderate intensity, equivalent to 5-6 on the CR 10 scale. They will then be encouraged to gradually incorporate periods of vigorous walking (7-8 CR10) towards the end of the programme. They will be asked to take around 5000 steps per day at the beginning of the programme, gradually increasing to > 7000 steps towards the end of the programme, depending on their physical condition.^[3]

Demonstrations and return demonstrations will be performed during the training to ensure that the participants are able to do the exercises properly. A YouTube video/pamphlet demonstrating the exercises used in this programme will be disseminated to all of the participants to encourage them to continually practice their exercises at home for at least 30 minutes at least 3 times per week. The participants will also be encouraged to perform 30–60 minutes of walking exercise at least 3 times per week. The intensity of the walking exercise should gradually increase from moderate to vigorous according to the CR10 scale. Information on exercising safely (Appendix 2) will be discussed with all of the participants prior to the beginning of the physical training.

Supervision of the physical training: Physical training will be conducted by a well-trained research assistant who will work as a physical trainer under the supervision of JL and RK. JL has successfully conducted many intervention studies using exercise to address different health problems among older people. JL and RK will also work closely with the physical trainer, to monitor the progress of each participant.

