The Control Condition: The same physical training and BCTs support will be arranged for the control group.

Instruments and Measures:

Participants will be assessed on a variety of outcomes (described below) at 1 week and at 1 and 3 months (T1 – T3) after the programme, which will be compared with the baseline assessment (T0). The participants will be asked to wear an ActiGraph Wgt3x accelerometer on their non-dominant wrist for 7 days before the commencement of any intervention, as well as during each outcome assessment time point.

Socio-demographic data: The following data will be collected: 1) data on age, gender, marital status, exercise habits, living conditions, and level of education, 2) the participants' health-related information, including their morbidities, cognitive status, medications, and number of hospital and out-patient clinic visits in the past 12 months.

Feasibility:

To understand the feasibility of this intervention, the frequency with which the participants in the experimental group use the tracker over the time of the study (i.e., 112 days), the recruitment rate, the attrition rate, the participants' adherence to the exercise regimen, and reports of adverse effects will be monitored.

Primary outcome measurement: Activity levels

The participants' physical activities and sedentary time will be objectively measured using a ActiGraph wGT3X accelerometer.

Secondary outcome measurements

Fitbit Data (only participants in the experimental group): The total steps per week, total walking distance per week, and time spent in different heart rate zones (50-69%, 70-84%, and >85% of the maximum heart rate) of an individual will be collected.

Physical Endurance: This will be evaluated using different physical tests:

1. The participants' lower-limb muscle and upper-limb strength will be assessed using a 30-second chair stand test and a handheld Jamar Hydraulic Hand Dynamometer, respectively.
2. Mobility will be assessed through the Timed-up-and-Go (TUG) test and by their gait speed (2-m walk). These two tests assess the overall performance of the lower limbs and walking speed, which can reflect the effect of exercise in enhancing the participants' overall physical endurance.

Exercise Self-efficacy: The participants' self-confidence in their ability to exercise in a variety of circumstances (e.g., even when they were feeling tired) will be assessed using the Chinese Self-Efficacy for Exercise scale (CSEE).

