Frailty status: This will be assessed based on Fried's frailty five phenotypes as mentioned in the sample inclusion criteria. **Physical activity level** is one criterion of frailty that will be assessed using the 10-item PASE-C to measure self-reported occupational, household, and leisure activities for the last week.

Self-reported sedentary behavioral and physical activity: This will be assessed using the Global Physical Activity Questionnaire-Chinese version (C-GPAQ), which comprises 16 questions designed to estimate an individual's self-perceived level of physical activity in three domains (occupational, transport-related and discretionary or leisure time).

Motivation to engage in physical activity: This will be assessed by the 19-item Chinese version of the Behavioral Regulation in Exercise Questionnaire-2 (C-BREQ-2). The C-BREQ-2 is a 19-item questionnaire assessing five dimensions: amotivation, external regulation, introjected regulation, identified regulation, and intrinsic regulation. Each item is rated on a 5-point scale ranging from 0 = "not true for me" to 4 = "very true for me", with higher scores indicative of higher motivation.

Procedures: Ethical and access approval will be obtained from the Ethics Review Committee of The University and study venues, respectively. Potential participants will be referred to the research team by the community centres. An RA will screen all potential participants for their eligibility to participate in this study. Written informed consent will then be obtained from all of the participants, to whom all aspects of the study will be explained and questions answered. They will then be interviewed to obtain their demographic data, and baseline assessment. After that, the participating community centres will be randomized to either the control or experimental group. Participants from each centre will be placed into their centre's corresponding group to avoid 'contamination' effects across participants. At 1 week, 1 month, and 3 months post-intervention, an independent assessor who is blinded to the group allocations will assess the participants' outcomes, which will be compared with the baseline assessment. Another RA will collect all "Fitbit activity-related data" from the participants in the experimental group every week. All of the participants in the experimental group will be invited to attend the focus group interviews, which will be conducted by JS after the first post-test T1 and T3.

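### Tracker use is to be measured over a 112-day study, but the protocol's own durations give 168 to 183 days from programme start to T3

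*Protocol*

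**What the plan says.** Under Feasibility, section B of the protocol lists five measures: tracker use in the experimental group, recruitment, attrition, adherence to the exercise regimen, and adverse effects. The first is how often participants "use the tracker over the time of the study (i.e., 112 days").

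The durations given elsewhere in section B are:

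- **Interventions:** "A 3-month exercise programme plus WAT intervention will be arranged for the participants in the experimental group". Support is then tapered and stopped, after which "Participants will be left to use the WAT on their own for 3 months during the follow-up period".
- **Physical training:** the weekly sessions "will be conducted for 12 weeks in the community centres".
- **Procedures:** outcomes are assessed "At 1 week, 1 month, and 3 months post-intervention". Instruments and Measures gives the same times and labels them T1 to T3.
- **Procedures:** Fitbit data are collected "from the participants in the experimental group every week", with no end date. Focus groups are held "after the first post-test T1 and T3".

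The SAP promises only descriptive statistics for feasibility and sets no window for tracker use.

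**The concern.** The protocol treats 112 days and the length of the study as the same thing, yet its own phases add up to considerably more. The days that a 112-day window from programme start would drop come late in the unsupported phase. The Background gives the reason for that phase: "these forms of support should be gradually withdrawn to see if the older people can use the WATs on their own". It also cites a study in which older users' ratings of their trackers declined between a supported phase and an independent one.

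A participant who wore the tracker every day to day 112 and then stopped would score 100% over 112 days, but only 61% to 67% over programme start to T3. A participant who wore it throughout would have more days of use than the stated window contains. Two analysts could therefore report different figures from the same data, in a study whose feasibility results are meant to inform a larger trial with longer follow-up.

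**Working it through.** **Inputs (protocol, section B)**

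- Programme: 12 weeks = 12 × 7 = 84 days (Physical training), or 3 months, taken as 91 days (Interventions).
- Unsupported tracker use: 3 months (Interventions), taken as 84 days if a month is 4 weeks, or 92 days by the calendar.
- T1, T2 and T3: 1 week, 1 month and 3 months after the programme (Instruments and Measures; Procedures).
- Assumption: the tracker is issued at programme start, and the 112 days are counted from that day.

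**Attempt to reproduce 112 days from programme start**

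| End of window | Sum | Days |
|---|---|---|
| End of programme | 12 weeks | 84 |
| T1 | 84 + 7 | 91 |
| T2, month = 4 weeks | 84 + 28 | **112** |
| T2, calendar months throughout | 4 months | 120 to 123 |
| T3, 3 months = 12 weeks in both phases | 84 + 84 | 168 |
| T3, 12 weeks + 3 calendar months | | 173 to 176 |
| T3, calendar months throughout | 91 + 92 | 183 |

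The calendar total varies from 181 to 184 with the start date; 183 is used below. The only exact match is 12 + 4 weeks, about T2. No version that runs to T3 gives 112.

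**What a 112-day window from programme start covers**

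- Share of the period to T3: 112/168 = 67%; 112/183 = 61%.
- Gap before T3: 168 − 112 = 56 days (8 weeks); 183 − 112 = 71 days (about 10 weeks).
- Unsupported days covered: 112 − 84 = 28, and 28/84 = 33%; 112 − 91 = 21, and 21/92 = 23%.
- Unsupported days left out: 56/84 = 67%; 71/92 = 77%.

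**Could the 112 days end at T3 instead?**

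The tracker would then have to be issued 112 − 84 = 28 or 112 − 92 = 20 days before the programme ends. That does not fit a 3-month programme delivered together with the tracker intervention.

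**The case against.** The best case for the plan is that this is one loosely worded number with little depending on it. Tracker use is only to be monitored. There is no formula, success threshold or decision rule, and the SAP treats feasibility descriptively. Weekly Fitbit collection has no stop date, and weekly steps, distance and heart-rate-zone time are secondary outcomes in their own right. Late disuse could therefore show there, or in the focus groups after T3. Because 112 days matches programme start to T2 exactly, a deliberate shorter window with careless wording is plausible. The tracker's issue date may also appear in Figure 1 or the study timeline, neither of which is shown in the text available here. Finally, no stated objective is tied to tracker use in the unsupported phase.

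Most of this stands as a limit on importance. It is why the percentages are conditional and why a shorter window must remain open to the sponsor. It does not remove the contradiction. Whatever the missing figure and timeline show, the Feasibility text calls 112 days the length of the study, while the assessment schedule in the same part of the protocol runs to 3 months after the programme. No legible text says that tracker monitoring stops at T2.

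**Conclusion.** The concern holds. The stated 112 days is not the length of the study on the protocol's own durations, which give 168 to 183 days from programme start to T3. That conclusion needs no assumption beyond how long a month is.

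The size of the effect does rest on an assumption. If the tracker is issued at programme start and the 112 days run from there, the measure misses the last 56 to 71 days, which is 67% to 77% of the unsupported phase.

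The consequence is limited to one descriptive feasibility measure in the experimental group. The primary outcome and the sample size are not affected. The correction should still be made, because this is the first-listed feasibility measure in a feasibility study and its denominator is at present ambiguous.

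**What to change.** Reconcile the Feasibility text with Interventions, Physical training and Procedures:

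1. Replace 112 days with the period from tracker issue to T3, and state its first and last day. If a window ending earlier, such as at T2, is intended, say so and stop describing it as the length of the study.
2. Confirm in Procedures that weekly Fitbit collection runs to T3.
3. Report tracker use separately for the programme phase and the unsupported phase, each over its own number of days. This goes beyond correcting the number, but it shows directly whether use holds up once support ends.
4. Put the same window in the SAP.

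The cost is a short text correction and slightly more tabulation. Only if weekly Fitbit collection was planned to stop before T3 would there be extra data collection.

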Several previous studies have demonstrated that activity tracker-based interventions can effectively increase physical activity among adolescents and young adults with or without chronic illnesses (Choi, Lee, Vittinghoff, & Fukuoka, 2016; Lyons, Swartz, Lewis, Martinez, & Jennings, 2017; Mendoza et al., 2017; Partridge, McGeechan, Bauman, Phongsavan, & Allman-Farinelli, 2017). For example, an RCT involving 51 inactive postmenopausal women showed that a 16-week wearable activity tracker-based intervention contributed to significantly increased MVPA and step counts when compared to the standard behavioural intervention

(Cadmus-Bertram, Marcus, Patterson, Parker, & Morey, 2015). However, evidence of the feasibility and acceptability of using WAT among older people remains scant.

A recent survey of 127 older people evaluated WAT positively in terms of comfort, ease of installation, and usefulness (Kekade et al., 2018). Another trial invited 32 older people (mean age: 64) to evaluate the usefulness of six types of trackers after wearing each for 3 days. WATs, in general, were perceived as useful and acceptable, and 70% of the participants planned to purchase a WAT in the future to focus on improving their physical activity levels (Mercer et al., 2016). Although promising, these initial studies assessed the experiences of older people who were relatively young, and over short durations, which may not represent long-term experiences or the experiences of frail older people.

Another study aimed to examine the short and long-term experiences of 95 older people using a WAT throughout the 8-month study. Their experiences were assessed after two main phases of the RCT: an intervention phase and a follow-up phase. During the 10-week intervention phase, the participants had regular contact with intervention staff and structured technical support for using their WAT. During the 6-month follow-up phase, the participants were left to use their own WAT independently. All ratings of the participants' experience of using WAT, which included "ease-of-use", "usefulness", and "acceptance", showed a downward trend between the intervention and follow-up phases. These findings indicate that older people may need more support to continue to use the WAT to the point of achieving increased MVPA (McMahon et al., 2016).

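### The Fitbit step and distance outcomes are weekly totals with no wear correction, so a change in days worn cannot be told apart from a change in activity

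*Protocol*

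**What the plan says.** Under Secondary outcome measurements, the protocol introduces "Fitbit Data (only participants in the experimental group") and names what will be gathered: "The total steps per week, total walking distance per week, and time spent in different heart rate zones". The weekly unit is attached to steps and distance. For heart-rate-zone time no unit is given.

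The Procedures section has a research assistant collect the Fitbit data weekly. It does not say whether those records are daily or already summed.

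Tracker use appears separately, under Feasibility: "the frequency with which the participants in the experimental group use the tracker over the time of the study (i.e., 112 days"). Nothing links it to the step, distance or zone outcomes.

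The step goal, under Physical training, is daily: "They will be asked to take around 5000 steps per day at the beginning of the programme", then "gradually increasing to > 7000 steps towards the end of the programme, depending on their physical condition".

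Under Interventions, help with the tracker is tapered and then stopped, and participants go on without it for three months. The Background cites a study of 95 older people in which ratings of the tracker "showed a downward trend between the intervention and follow-up phases".

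The SAP does not mention Fitbit data. Neither document contains a valid-day rule, a minimum wear time or an average per worn day.

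**The concern.** If an unworn day contributes nothing, a weekly total falls when the tracker stays in a drawer, just as it falls when the wearer walks less. The two explanations lead to different decisions. If wear fell, the larger study that the protocol foresees would need a different support schedule or device. If activity fell, the intervention itself would be in question.

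The Background treats independent use as something to be found out: support is removed to see whether older people manage the tracker alone. A measure that merges use with activity answers neither question cleanly. Nothing else fills the gap week by week, because the ActiGraph is worn for seven days at baseline and at each outcome assessment only.

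**Working it through.** **Inputs from the documents**
- Step goal: about 5000 per day at the start and above 7000 towards the end of the programme (Protocol, Physical training).
- Outcome unit: weekly total for steps and distance (Protocol, Secondary outcome measurements).
- Tracker-use window: 112 days (Protocol, Feasibility).
- Programme of 12 weeks (Physical training), then 3 months without support (Interventions).

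**Assumptions, not in the documents**
- Unworn days record no steps.
- The tracker is worn 7 days a week at the start and 7 down to 3 at the end.
- Three months is taken as 91 days.

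The documents state no weekly total or wear rate, so there is no figure of the plan's own to reproduce.

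**Step 1: the metric.** Recorded weekly steps = steps per worn day × days worn.

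**Step 2: a true rise from 5000 to 7000 per day.** The start is 5000 × 7 = 35,000 a week. The true gain is 2000/5000 = 40%.

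| Days worn at end | Recorded total (7000 × days) | Apparent change from 35,000 | Total ÷ days worn |
|---|---|---|---|
| 7 | 49,000 | +40% | 7000 |
| 6 | 42,000 | +20% | 7000 |
| 5 | 35,000 | 0% | 7000 |
| 4 | 28,000 | -20% | 7000 |
| 3 | 21,000 | -40% | 7000 |

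**Step 3: break-even.** The gain disappears when end wear is 5000/7000 = 71.4% of starting wear. That is 5.0 days from a start of 7, 4.3 from 6 and 3.6 from 5. Because the end goal is above 7000, higher levels were tried with a start of 7 days: 35,000/7500 = 4.7 days and 35,000/8000 = 4.4 days.

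**Step 4: no change in walking.** This case fits the unsupported period best. At a constant 7000 per day, wear falling from 7 to 4 days takes the total from 49,000 to 28,000. Since 28,000/49,000 = 0.571, that reads as a 43% fall.

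**Step 5: can the use measure repair this later?** Programme plus follow-up is 84 + 91 = 175 days, and 112/175 = 64%. If the 112 days run from the start of the programme, which the protocol does not say, they reach 112 - 84 = 28 days into follow-up. The other 91 - 28 = 63 days would have no planned wear measure.

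**Step 6: the alternative metric.** The last column of the table stays at 7000 whatever the wear, provided that worn days resemble unworn ones.

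**The case against.** The strongest reply is that activity is measured elsewhere. The primary outcome comes from the ActiGraph, in both arms, at baseline and at 1 week, 1 month and 3 months after the programme. Two questionnaires, the C-GPAQ and the PASE-C, add self-report. This stands. A reader might infer that the trial could not tell whether activity lasts once support ends, or that a real gain would be hidden from it. The documents do not support that: only the weekly Fitbit series is blurred.

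A second reply is that falling wear is not established. This also stands. A reader might take the protocol to predict it, but the cited decline is in ratings of ease, usefulness and acceptance in another cohort, not in wear. Listing tracker use as a feasibility measure does not forecast a fall either. The series also need not fall: at 5 of 7 days it is flat, and at 6 it still shows half the gain.

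Third, the timing differs. The step increase is due within the 12-week programme, while the argument for wear loss rests mainly on the period afterwards. Support does taper earlier, so some overlap is possible, but weekly data could show a gain made before wear dropped. Step 2 therefore shows how the metric behaves and is not a forecast.

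Finally, the protocol describes collection, and the SAP names no test on these totals. Its silence is not a decision to analyse uncorrected sums. Even so, weekly totals are the named outcome and no other Fitbit metric is planned. The daily goal against a weekly total is, by itself, only a matter of units and is not a separate fault.

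**Conclusion.** The concern holds for a secondary, single-arm outcome. As defined, the weekly totals confound wear with activity, and no correction is planned. Heart-rate-zone time depends on wear in the same way, whatever its unit. The primary outcome and the comparison between arms are untouched.

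The arithmetic is certain, but the amount of wear loss is not. Under the stated assumptions, wear of 6 down to 3 days moves the apparent change for a true 40% rise from +20% to -40%, and a loss of 3 days a week at constant activity imitates a 43% fall. The point deserves correction because this is the only weekly record through the unsupported months, and its reading could shape the larger study. It does not threaten the trial's main conclusion.

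**What to change.** - Replace the weekly totals with mean steps and mean distance per valid wear day, and express heart-rate-zone time the same way.
- Define a valid day in the SAP before analysis, for example by a minimum number of hours with a recorded heart rate. Set a minimum number of valid days for a week to enter the trend.
- Show days worn per week beside every Fitbit summary.
- Extend the tracker-use measure from 112 days to the end of the unsupported follow-up, and state the day on which it starts.

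The cost is mainly wording, on one condition: the sponsor must confirm that the weekly collection keeps day-level records (and within-day records, if the rule uses hours). The protocol does not say so. If only weekly sums are kept, the export procedure has to change as well.

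There are two statistical costs. Weeks with little wear become missing instead of counting as low activity. Worn days may also be unlike unworn ones: if people put the tracker on for active days, the daily mean overstates their activity. That is why days worn must always be shown with it.
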